9.1.3. Pulmonary Function Test

Spirometry equipment and a device to measure FeNO (see Section 9.1.4) will be provided to all sites by a third-party vendor. Spirometry data from this study will be analysed by a third-party vendor. Details on performing the spirometry assessments, including information on the equipment provided and its use as well as specific instructions on performing the spirometry manoeuvres are documented in the SRM and the third-party vendor manual.

9.1.3.1. Spirometry

Spirometry will be performed to assess FEV1 and FVC. At least 3 spirometry manoeuvres (from a maximum of 8 attempts) should be achieved on each occasion that spirometry assessments are performed. For spirometry data collected at Screening (Visits 1), the best spirometry effort will be selected from a measurement that meets American Thoracic Society (ATS)/ European Respiratory Society (ERS) guidelines and has a minimum of 2 efforts which are considered valid and repeatable, in accordance with the ATS/ERS standards [Miller, 2005]. Measurements with 3 valid but non-repeatable efforts will not be accepted. For spirometry data collected during the Treatment Period (Visits 2) - 11, including EW visit), the best spirometry effort will be selected from a measurement that meets ATS/ERS guidelines and has a minimum of 2 efforts which are considered valid (not necessarily repeatable). As always, sites should continue to strive to collect at least 3 valid (with no more than 8) efforts, as per ATS/ERS guidelines. At each visit, spirometry assessments must be performed at the same time of day (± 2 hour) as the assessment performed at Visit 2 (the baseline assessment). Participants should withhold short-acting beta-2-agonists (SABAs) for ≥ 6 hours and LABAs for ≥ 1 dosing interval (i.e. ≥ 12 or ≥ 24 hours based on the prescribed dosing interval of the product) prior to the clinic visit, if possible.

9.1.3.2. Reversibility

All reversibility evaluations should follow the recommendations of the ATS/ ERS Task force: Standardization of Lung Function Testing [Miller, 2005]. A baseline spirometry assessment should be performed after a washout period of at least 6 hours for short-acting β_2 - agonists and 1 dosing interval for long-acting β_2 -agonists (or fixed dose combinations of LABA and ICS).

To perform the reversibility assessment, 4 puffs of the provided salbutamol/albuterol is administered following completion of the baseline assessment. A spacer device may be used for testing, if required. A second spirometry assessment is performed within 10 to 15 minutes after administration of the salbutamol/albuterol.

Reversibility assessment at Screening (Visit 1) is not required if there is documented reversibility prior to Screening (Visit 1), or documented history of bronchial hyperreactivity from a bronchoprovocation study (e.g. methacholine challenge) prior to Screening (Visit 1).

9.1.4. Fractional Exhaled Nitric Oxide (FeNO)

FeNO will be measured using a handheld electronic device. Measurements will be obtained in accordance with the ATS/ERS Recommendations for Standardized Procedures for the Online and Offline Measurement of Exhaled Lower Respiratory Nitric Oxide and Nasal Nitric Oxide [Miller, 2005]. All sites will use standardized equipment provided by a central vendor. For each observation, at least 2 measurements will be obtained to establish reproducibility (up to 8 measurements can be performed). FeNO measurements will be interpreted in accordance with the Official ATS Clinical Practice Guideline: Interpretation of Exhaled Nitric Oxide Levels (FeNO) for Clinical Applications [Dweik, 2011]. FeNO observations must be completed before FEV1 assessments. Participants should not use their rescue medication for at least 6 hours before each FeNO assessment, unless essential for clinical need. Participants should also withhold LABAs for ≥1 dosing interval (i.e. ≥12 or ≥24 hours based on the prescribed dosing interval of the product) before each FeNO assessment.

9.1.5. Review of Loss of Asthma Control

Loss of asthma control is defined as at least one of the following:

- ACQ-5 score increase from baseline (measured at the end of Run-in) ≥0.5 point) or
- Pre-bronchodilator FEV1 decrease from baseline (measured at the end of Run-in) > 7.5 % or
- Inability to titrate inhaled corticosteroid according to the pre-defined schedule (Section 5.1) or
- A clinically significant asthma exacerbation (requiring OCS and/or hospitalisation.

At each clinic visit, the Investigator will utilize clinical discretion and available objective evidence (including but not limited to eDiary data, spirometry data, the most recent ACQ5 scores, history of exacerbations, conmeds, AEs) to determine if the patient is experiencing loss of asthma control. The paper Medical Problems/Medications Taken worksheet must also be reviewed by the Investigator (or appropriately trained designee) at each visit to the study site to assist the Investigator in the identification of loss of asthma control. It is expected that the Investigator will indicate which criterion (criteria) the subject met that constituted loss of asthma control.

9.2. Adverse Events

The definitions of an AE or SAE can be found in Appendix 4.

Asthma exacerbations or worsening of asthma should not be recorded as an AE, unless they meet the definition of an SAE. For the purposes of this study, asthma exacerbations

will be collected and recorded on the exacerbations log in the eCRF. The treatment details must also be recorded in the eCRF. The time period for collection of asthma exacerbations will begin from screening and will end after the follow-up period has been completed.

The investigator and any designees are responsible for detecting, documenting, and reporting events that meet the definition of an AE or SAE and remain responsible for following up AEs that are serious, considered related to the study treatment or the study, or that caused the participant to discontinue the study treatment (see Section 8).

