8. DISCONTINUATION CRITERIA

8.1. Discontinuation of Study Treatment

Participants that permanently stop study treatment are encouraged to remain in the study. Participants have the right to discontinue study treatment before the end of the study. A participant may also be asked to discontinue study treatment at the Investigator's discretion.

Participants who withdraw from study treatment prematurely (for any reason) should, where possible, continue to be followed-up until the completion of the Safety Follow-up assessments:

• For participants who discontinue IP early, but have not withdrawn consent to participate in the study, an early withdrawal (EW) visit will be performed 4 weeks after the last dose of blinded study treatment. These participants should continue in the study and complete all assessments at the remaining protocol-defined visits until their EW visit. Participants should resume regular treatment for their asthma, as determined by the investigator. Three Follow-up visits will then be performed 4, 8, and 12 weeks after the EW visit for safety assessments.

CONFIDENTIAL

• Participants who discontinue IP early and withdraw consent to participate in the study should complete as many assessments planned for the EW visit as possible.

If this is not possible, the Investigator must encourage the participant to participate in as much of the study as they are willing (or able) to.

A participant may be withdrawn from study treatment at any time. A reason for premature discontinuation of study treatment (e.g., AE, lack of efficacy [including loss of asthma control], protocol deviation, Investigator discretion, consent withdrawn etc.) must be captured in the eCRF.

A participant must be withdrawn from study treatment if any of the following stopping criteria are met:

- 1. Liver Chemistry: Meets any of the protocol-defined liver chemistry stopping criteria.
- 2. QTc: Meets any of the protocol-defined stopping criteria.
- 3. Pregnancy: Positive pregnancy test.
- 4. Participant meets at least one of the following criteria for 'loss of asthma control':
 - ACQ-5 score increase from baseline (measured at Visit 2) \geq 0.5 point.
 - Pre-bronchodilator FEV1 decrease from baseline (measured at Visit 2) >7.5 %.
 - Inability to continue inhaled corticosteroid titration which is assessed and determined by the investigator at any time point following randomization, including on scheduled clinic visits.

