- Signs, symptoms, or the clinical sequelae of a suspected overdose of either study treatment or a concomitant medication. Overdose per se will not be reported as an AE/SAE unless it is an intentional overdose taken with possible suicidal/selfharming intent. Such overdoses should be reported regardless of sequelae.
- "Lack of efficacy" or "failure of expected pharmacological action" per se will not be reported as an AE or SAE. Such instances will be captured in the efficacy assessments. However, the signs, symptoms, and/or clinical sequelae resulting from lack of efficacy will be reported as AE or SAE if they fulfill the definition of an AE or SAE.
- The signs, symptoms, and/or clinical sequelae resulting from lack of efficacy will be reported as AE or SAE if they fulfill the definition of an AE or SAE. Also, "lack of efficacy" or "failure of expected pharmacological action" constitutes an AE or SAE.

Events NOT Meeting the AE Definition

- Any clinically significant abnormal laboratory findings or other abnormal safety assessments which are associated with the underlying disease, unless judged by the investigator to be more severe than expected for the participant's condition.
- The disease/disorder being studied or expected progression, signs, or symptoms of the disease/disorder being studied, unless more severe than expected for the participant's condition.
- Medical or surgical procedure (eg, endoscopy, appendectomy): the condition that leads to the procedure is the AE.
- Situations in which an untoward medical occurrence did not occur (social and/or convenience admission to a hospital).
- Anticipated day-to-day fluctuations of pre-existing disease(s) or condition(s) present or detected at the start of the study that do not worsen.

Definition of SAE

If an event is not an AE per definition above, then it cannot be an SAE even if serious conditions are met (eg, hospitalization for signs/symptoms of the disease under study, death due to progression of disease).

A SAE is defined as any untoward medical occurrence that, at any dose:

a. Results in death

b. Is life-threatening

The term 'life-threatening' in the definition of 'serious' refers to an event in which the participant was at risk of death at the time of the event. It does not refer to an event, which hypothetically might have caused death, if it were more severe.

c. Requires inpatient hospitalization or prolongation of existing hospitalization

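### Section 9.2 and Appendix 4 conflict on whether a hospitalised asthma exacerbation is an SAE, and Appendix 4 contradicts itself on lack of efficacy

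*Protocol*

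**What the plan says.** All of the following stands in the current amendment.

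- **Section 9.2 (Adverse Events)** refers to Appendix 4 for the AE and SAE definitions, then sets a rule for this trial: "Asthma exacerbations or worsening of asthma should not be recorded as an AE, unless they meet the definition of an SAE". Exacerbations go on a dedicated eCRF log, with treatment details, from screening to the end of follow-up.
- **Appendix 4, Definition of SAE**, opens with a condition: "If an event is not an AE per definition above, then it cannot be an SAE even if serious conditions are met". Its examples are "hospitalization for signs/symptoms of the disease under study, death due to progression of disease". Criterion c of the list that follows is "Requires inpatient hospitalization or prolongation of existing hospitalization".
- **Appendix 4, Events Meeting the AE Definition**, includes a worsening, in frequency or intensity, of a condition the participant already had.
- **Appendix 4, Events NOT Meeting the AE Definition**, includes the disease being studied and its "expected progression, signs, or symptoms of the disease/disorder being studied, unless more severe than expected" for that participant.
- **Appendix 4 on lack of efficacy**: one bullet says that it "per se will not be reported as an AE or SAE. Such instances will be captured in the efficacy assessments". The next bullet ends by saying that it "constitutes an AE or SAE". Both allow resulting signs, symptoms and sequelae to be reported if they meet the AE or SAE definition.
- **Section 8.1** gives as separate reasons for stopping treatment "AE, lack of efficacy [including loss of asthma control], protocol deviation".

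**The concern.** Section 9.2 decides whether to record an AE by asking whether the event is an SAE. Appendix 4 decides whether an event is an SAE by first asking whether it is an AE. The printed example then names almost exactly the event that Section 9.2 means to bring in: a hospital admission for asthma in an asthma trial.

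This design makes the case a practical one. Inclusion criterion 7 requires an exacerbation in the previous 12 months that needed systemic corticosteroid and/or hospitalisation. Section 5.1 then withdraws the LABA and steps the inhaled steroid down to nothing. Exacerbations needing oral steroid or admission are a component of the primary endpoint.

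SAE status triggers reporting to the sponsor within 24 hours (Section 9.2.1) and entry into the non-fatal SAE summary and the SAE narratives (Section 10.4.2). SAEs are also among the data named for the independent safety review committee (Section 5.1). If sites classify the same event differently, the SAE tables partly reflect site interpretation.

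**Working it through.** There is no figure in the plan to reproduce and no arithmetic to run. The check is to follow one event through the text: a participant admitted overnight for an asthma exacerbation during the steroid step-down.

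**Reading A: reported as an SAE.**
1. Asthma is a pre-existing condition that has worsened in intensity, so the event meets the AE definition in Appendix 4.
2. As an AE, it passes the opening condition of the SAE definition.
3. It required admission, so criterion c is met and it is an SAE.
4. Section 9.2 exempts exacerbations from AE recording unless they are SAEs. This one is, so it is recorded and reported within 24 hours.

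**Reading B: not reported as an SAE.**
1. Asthma is the disease being studied. Given criterion 7 and the withdrawal of controller therapy, the investigator judges the exacerbation to be within what was expected, so it falls under the events that do not meet the AE definition.
2. As a non-AE, it cannot be an SAE even though it is serious. The printed example confirms this for an admission caused by the disease under study.
3. The Section 9.2 exception is not triggered. The event goes on the exacerbation log only.

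Each reading follows current text at every step. They part at step 1, where Appendix 4 offers two applicable entries with opposite results and no rule for choosing. The qualifier about severity beyond expectation does not settle the choice, because the protocol does not define the expected severity.

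**What differs downstream.** Under A the event enters 24-hour reporting, the non-fatal SAE summary and an SAE narrative. Under B it enters none of these. Under both it is on the exacerbation log and counts towards the primary endpoint, so the efficacy analysis is the same.

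**Deaths.** The same classification question arises, but capture does not depend on it. Section 9.2.5 requires the death section of the eCRF for every death, whether or not it is an SAE, within one week of the report. Section 10.4.2 requires narratives for deaths as well as for SAEs.

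**Lack of efficacy.** One bullet sends it to the efficacy assessments and not to AE/SAE reporting; the next makes it an AE or SAE. Both cannot be followed. Section 8.1 treats lack of efficacy, including loss of asthma control, as a reason distinct from an AE, and Section 9.2 keeps non-serious asthma worsening off the AE page. Both fit only the first bullet.

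**The case against.** The strongest reply is that Section 9.2 is a recording rule and does not redefine an AE. An exacerbation can be an AE under Appendix 4 and simply be exempt from the AE page unless serious. That is Reading A, and it is coherent. Section 9.2 is also specific to this trial and names asthma, whereas the Appendix 4 example is generic. Elsewhere Appendix 4 leans towards reporting: doubt about whether hospitalisation occurred or was necessary is resolved towards serious, and intensive emergency treatment for allergic bronchospasm is listed as usually serious. Section 5.4 adds that the safety assessments are meant to make actual exacerbations less likely, so an admission is arguably not the expected course.

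Much of this stands. The intent of Section 9.2 is clear, and the rule is not hopelessly circular. But its exception relies on the Appendix 4 SAE definition, and that definition contains the example pointing the other way. The leaning towards seriousness also comes after the opening condition that the event be an AE.

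Three stronger inferences are tempting, and the documents do not support them:

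- **That unexpected severity is the only way in.** It is not. Worsening of a pre-existing condition is listed as an AE, and both lack-of-efficacy bullets allow resulting signs and sequelae to be reported where they meet the definition.
- **That these events would be lost to oversight.** Deaths have their own form and narratives. The exacerbation log records treatment, and hospitalisations or ER visits are a secondary endpoint. The review committee's data are expressly not confined to SAEs, and its charter is not at hand.
- **That the harm can be sized from an assumed event rate in the 148 randomised participants.** That would give the chance that some hospitalised exacerbation occurs, not that one is misclassified. The protocol supplies neither quantity.

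**Conclusion.** The wording is at fault as written, to a minor to moderate degree, and the fault concerns safety reporting. Taken literally, the Appendix 4 example keeps a hospitalised exacerbation out of 24-hour SAE reporting and the SAE summaries, against the evident purpose of Section 9.2, while another entry in the same appendix lets it in. The expected consequence is possible inconsistency between sites for non-fatal hospitalised exacerbations. The primary endpoint, sample size and power are untouched.

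The lack-of-efficacy contradiction is plain on the page but has little demonstrated effect, because Sections 8.1 and 9.2 already point to the first bullet.

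The conclusion assumes that sites work from the protocol text. Site guidance outside the protocol might already settle the matter; it is not at hand.

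**What to change.** 1. In Section 9.2 and in Appendix 4, state that any asthma exacerbation meeting one or more of seriousness criteria a to f is an AE and is reported as an SAE, whether or not its severity was expected. Exacerbations meeting none of them stay on the exacerbation log only.
2. In the Appendix 4 definition of an SAE, remove the example about hospitalisation or death from the disease under study, or exempt asthma from it.
3. In Appendix 4, delete the closing sentence of the second lack-of-efficacy bullet, which makes lack of efficacy itself an AE or SAE. Keep the first bullet.

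The cost is a few edited sentences and a note to sites. No new data are collected, no analysis changes, and no reporting duty is created beyond what Section 9.2 already intends.

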9.2.1. Time Period and Frequency for Collecting AE and SAE Information

- All SAEs will be collected from the Visit 2 until the last follow-up visit at the time points specified in the SoA (Section 2). At Visits 0 and 1 SAE information will be collected only for any SAEs considered as related to study participation.
- All AEs will be collected from the signing of the ICF until the follow-up visit at the time points specified in the SoA (Section 2).
- Medical occurrences that begin before the start of study treatment but after obtaining informed consent will be recorded on the Medical History/Current Medical Conditions section of the case report form (eCRF) not the AE section.
- All SAEs will be recorded and reported to the sponsor or designee within 24 hours, as indicated in Appendix 4. The investigator will submit any updated SAE data to the sponsor within 24 hours of it being available.
- Investigators are not obligated to actively seek AEs or SAEs in former study participants. However, if the investigator learns of any SAE, including a death, at any time after a participant has been discharged from the study, and he/she considers the event to be reasonably related to the study treatment or study participation, the investigator must promptly notify the sponsor.
- The method of recording, evaluating, and assessing causality of AEs and SAEs and the procedures for completing and transmitting SAE reports are provided in Appendix 4.

9.2.2. Method of Detecting AEs and SAEs

Care will be taken not to introduce bias when detecting an AE and/or SAE. Open-ended and non-leading verbal questioning of the participant is the preferred method to inquire about AE occurrence. Appropriate questions include:

- "How are you feeling?"
- "Have you had any (other) medical problems since your last visit/contact?"
- "Have you taken any new medicines, other than those provided in this study, since your last visit/contact?"

Participants will be issued with a paper Medical Problems/Medications Taken worksheet to record any medical problems experienced and medications used during the study (See Section 9.1.2).

9.2.3. Follow-up of AEs and SAEs

After the initial AE/SAE report, the investigator is required to proactively follow each participant at subsequent visits/contacts. All SAEs will be followed until the event is resolved, stabilized, otherwise explained, or the participant is lost to follow-up (as defined in Section 8.3). Further information on follow-up procedures is given in Appendix 4.

9.2.4. Regulatory Reporting Requirements for SAEs

- Prompt notification by the investigator to the sponsor of a SAE is essential so
 that legal obligations and ethical responsibilities towards the safety of
 participants and the safety of a study treatment under clinical investigation are
 met.
- The sponsor has a legal responsibility to notify both the local regulatory authority and other regulatory agencies about the safety of a study treatment under clinical investigation. The sponsor will comply with country-specific regulatory requirements relating to safety reporting to the regulatory authority, Institutional Review Boards (IRB)/Independent Ethics Committees (IEC), and investigators.
- Investigator safety reports must be prepared for suspected unexpected serious adverse reactions (SUSAR) according to local regulatory requirements and sponsor policy and forwarded to investigators as necessary.
- An investigator who receives an investigator safety report describing a SAE or
 other specific safety information e.g. summary or listing of SAEs from the
 sponsor will review and then file it along with the Investigator's Brochure and
 will notify the IRB/IEC, if appropriate according to local requirements.

9.2.5. Cardiovascular and Death Events

For any cardiovascular events detailed in Appendix 4 and all deaths, whether or not they are considered SAEs, specific Cardiovascular (CV) and Death sections of the eCRF will be required to be completed. These sections include questions regarding cardiovascular (including sudden cardiac death) and non-cardiovascular death.

The CV eCRFs are presented as queries in response to reporting of certain CV Medicinal Dictionary for Regulatory Activities (MedDRA) terms. The CV information should be recorded in the specific cardiovascular section of the eCRF within one week of receipt of a CV Event data query prompting its completion.

The Death eCRF is provided immediately after the occurrence or outcome of death is reported. Initial and follow-up reports regarding death must be completed within one week of when the death is reported.

